4. CHANGES IN THE PLANNED ANALYSIS OF THE STUDY

The testing on the hypothesis of flat dose response curve that described in CTP will not be performed

In addition, model-based analysis of primary endpoint (trough FEV1 % predicted) and secondary endpoint (LCI),

For secondary endpoint (LCI), an analysis of covariance (ANCOVA) will be used to compare the change from baseline of LCI after 4 weeks of treatment. Other endpoints including patient reported outcomes (CASA-Q and CFQ-R) will be summarized descriptively for all dose levels.

age effect (adult versus adolescent) will be removed from the statistical model.

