6. GENERAL ANALYSIS DEFINITIONS

6.1 TREATMENT(S)

For basic study information on treatments to be administered please refer to Section 4 of the CTP.

Patient randomisation will start with only adult patients to either 200 µg bid of BI 1265162 or placebo in a 1:1 ratio. Enrolment of adolescent patients will be based on periodic reviews of adult patient safety data. The analysis plan for periodic safety reviews of adult patients will be described separately.

As soon as 28 patients are allocated to these two treatment arms, the remaining patients will be allocated to the other doses of BI 1265162 as well as the highest dose and placebo in a 1:1:1:1:1 ratio (14 patients per treatment arm). As a result, it was planned to have patients distributed in a 2:1:1:1:2 ratio (2 for either placebo or 200 µg bid of BI 1265162 and 1 for other doses of BI 1265162) with around 20% of adolescents per group.

Patients will be analysed according to [Table 6.3: 1](#). All planned analysis will be presented by this treatment group, unless specified otherwise. Handling of patients where treatment assignment has not been followed will be handled on a case-by-case basis, to be agreed at report planning meetings or DBL meeting (but prior to database lock).

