7.4.1 Primary analysis of the primary endpoint(s)

To account for the repeated nature of the data and the covariates in the nature, a restricted maximum likelihood (REML) based approach using a mixed model with repeated measurements (MMRM) will be carried out comparing the change from baseline in percent predicted trough FEV1 percent predicted at 4 weeks of treatment.

The analysis will include the fixed, categorical effects of treatment at each visit and the fixed continuous effects of baseline at each visit. Visit will be treated as the repeated measure with an unstructured covariance structure used to model the within-patient measurements. The model will only include data from highest dose level and placebo because of limited sample size from other dose levels.

The Kenward-Roger approximation will be used to estimate denominator degrees of freedom and adjust standard errors.

The MMRM analysis will be carried out in SAS and covariate-adjusted fixed effect estimates of average response for each dose group and the covariance matrix will be extracted from the fit.

The following SAS[®] code for MMRM will be used:

```
PROC MIXED DATA=alldata cl method=reml ocovtest;
  CLASS usubjid trtpso avisitn;
  MODEL ept = trtpso*avistin base*avistin /ddfm=kr solution;
  REPEATED avisitn /subject=usubjid type UN r rcorr;
  LSMEANS trtpso*avistin / pdiff=all om cl alpha=0.05;
RUN;
```

If the model failed to converge, the following covariance structures will be tested in order: UN → AR(1).

For subgroup analysis, same MMRM model will be carried out within each subgroup.

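### Is it a flaw that the SAP refits the MMRM in each subgroup and plans no estimate of how the effect differs between subgroups?

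*SAP*

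**What the plan says.** The subgroup method in SAP Section 7.4.1 is a single sentence: "For subgroup analysis, same MMRM model will be carried out within each subgroup". The model refitted is the primary one, with treatment-by-visit and baseline-by-visit terms only: "MODEL ept = trtpso*avistin base*avistin /ddfm=kr solution". It therefore contains no subgroup term and no treatment-by-subgroup interaction. The output request is "LSMEANS trtpso*avistin / pdiff=all om cl alpha=0.05", which gives pairwise differences with 95% limits and, by default, two-sided p-values. Two arms enter the model: "The model will only include data from highest dose level and placebo because of limited sample size from other dose levels". Each subgroup fit thus gives one treatment difference at Week 4, between 200 µg bid and placebo.

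No available section names a subgroup factor. The one factor that comes to mind is age group, but Section 4 says that the "age effect (adult versus adolescent) will be removed from the statistical model", and Section 7.5.2.4 records that no adolescents were randomised.

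**The concern.** Subgroup results are usually read to judge whether a treatment effect is consistent. Separate fits show each effect but not the difference between them, nor how precisely that difference is known. Readers often fill the gap by setting p-values side by side: significant here, not significant there, so the effect must differ. That reasoning is invalid, because a smaller subgroup can miss significance through lack of power alone. In a trial of this size such a pattern would be common even with one common effect. If the SAP relied on that reasoning, the report could claim a differential effect that the data do not support.

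**Working it through.** **1. Planned numbers.** Section 6.1 describes two allocation stages. In the first, 28 patients go 1:1 to 200 µg bid or placebo, which is 14 per arm: "As soon as 28 patients are allocated to these two treatment arms, the remaining patients will be allocated to the other doses". The second allocates "in a 1:1:1:1:1 ratio (14 patients per treatment arm").

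- 200 µg bid and placebo: 14 + 14 = 28 each
- each other dose: 14
- total: 28 + 14 + 14 + 14 + 28 = 98

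This reproduces the SAP's own figure: "it was planned to have patients distributed in a 2:1:1:1:2 ratio". The MMRM would use 28 per arm if the plan was met; actual numbers are not given.

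**2. How often would p-values disagree under a common effect?** The SAP gives no power, SD, number of subgroups or split, so all of these are assumed. Let *d* be the overall effect divided by its standard error, fixed by the assumed overall power *P*. A subgroup holding a share *f* of the patients has non-centrality *d*√*f*. If *a* and *b* are the powers in the two subgroups, then

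P(exactly one significant) = *a*(1 − *b*) + *b*(1 − *a*).

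Example with *P* = 0.80, where *d* = 1.960 + 0.842 = 2.802:

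- Equal halves: *d*√0.5 = 1.981, so *a* = *b* = 0.508 and the probability is 2 × 0.508 × 0.492 = 0.500.
- 80:20: *d*√0.8 = 2.506 gives *a* = 0.707; *d*√0.2 = 1.253 gives *b* = 0.240; the probability is 0.707 × 0.760 + 0.240 × 0.293 = 0.608.

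| Overall power | Equal halves | 80:20 |
|---|---|---|
| 0.30 | 0.287 | 0.299 |
| 0.50 | 0.406 | 0.441 |
| 0.80 | 0.500 | 0.608 |
| 0.90 | 0.466 | 0.627 |
| 0.99 | 0.244 | 0.516 |

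With no effect in either subgroup the figure is 2 × 0.05 × 0.95 = 0.095. The arithmetic behind the worry is sound. It is the error rate of one rule: declare a difference when one p-value is below 0.05 and the other is not. No available section of the SAP states that rule.

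**3. Is the information missing?** Subgroups contain different patients, so separately fitted estimates are independent, and

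SE(difference between subgroups) = √(SE₁² + SE₂²).

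The inputs come from the planned fits: Section 7.4.1 already asks for estimates, confidence limits and Kenward-Roger degrees of freedom. A reader of the report can form the contrast without a new model.

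**4. What would the contrast show?** In units of the residual SD, with equal variances, complete data and 28 per arm:

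- Overall SE: √(1/28 + 1/28) = 0.267.
- Halves of 14 per arm: each SE = √(1/14 + 1/14) = 0.378; the difference has SE √(0.378² + 0.378²) = 0.535, which is 2.0 times the overall SE.
- For an 80:20 split the ratio is √(1/0.8 + 1/0.2) = √6.25 = 2.5.

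Power for an interaction as large as the overall effect, at 80% overall power:

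- Halves: 2.802/2.0 = 1.401, and Φ(1.401 − 1.960) = 0.288.
- 80:20: 2.802/2.5 = 1.121, which gives 0.202.

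A small-sample simulation of the Week 4 analysis gave slightly less: 0.271 for two subgroups of 14 per arm and 0.180 for subgroups of 22 and 6 per arm. The contrast would mostly display wide uncertainty, which the wide subgroup intervals already signal.

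**5. Can the silence be held against the plan?** The subgroup sentence presupposes subgroups that are defined somewhere, yet no available section defines any. Sections 6.4, 7.1 to 7.3 and 7.6 are absent from the public text, Section 4 breaks off in mid-sentence, and the protocol is not available. A rule for comparing subgroups could stand in any of these places.

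**The case for a change.** The strongest reply is that the SAP itself fixes the subgroup method, so the point is not simply left to the protocol. Subgroup analysis exists mainly to judge consistency, and side-by-side estimates with p-values invite exactly the misreading quantified above. One sentence and one derived line per comparison would guard against it, and low interaction power is an argument for showing the uncertainty.

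Part of this stands. The separate fits do not by themselves show whether effects differ, the disagreement rates are correct under their assumptions, and an exploratory difference with its confidence interval would be cheap and sensible to report. None of that shows an error. The guard is against something a reader might do, whereas the plan prescribes no such comparison. The 80:20 figures, which are the largest, match no usable subgroup: the only 20% share in the document is the planned adolescent share in Section 6.1, and no adolescents were randomised.

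**Conclusion.** The concern does not hold. Following Section 7.4.1 as written gives valid within-subgroup estimates and intervals and leaves the primary analysis unchanged; the size of the error in any planned result is nil. The 24–63% range describes a misuse that the available text does not plan, for assumed power, assumed splits and no named subgroup factor. The contrast in question recombines output already planned and, at about 18–29% power in the cases worked, would rarely alter a conclusion. Adding it is a reporting preference.

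This rests on the available text only. The judgement would change if the withheld sections, the protocol or the trial report inferred a difference between subgroups from one p-value falling below 0.05 and another above it.

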7.5 SECONDARY ENDPOINT(S)

7.5.1 Key secondary endpoint(s)

Not applicable.

7.5.2 Secondary endpoint(s)

7.5.2.1 Analysis of LCI

An analysis of covariance (ANCOVA) will be used to compare the change from baseline of LCI after 4 weeks of treatment with adjustment for categorical effects of treatment and the fixed continuous effect of baseline. The model will include data from highest dose level and placebo. Descriptive analysis will be performed for other dose levels.

Tables and/or spaghetti plots will display individual LCI values over time. In addition, a waterfall plot for change from baseline at Week 4 will be presented.

7.5.2.2 Safety endpoints

For analysis for AE, refer [Section 7.8.1](#).

7.5.2.3 Pharmacokinetic endpoints

The PK analysis of secondary endpoints will be based on the PKS. For each of dose proportionality of secondary endpoints ($C_{max,N}$, $C_{pre,N}$ and $AUC_{0-t,N}$), displaying geometric means of pairwise ratios together with 95% confidence intervals will be provided by dose group. Additional PK, PKPD modelling will be defined in a separate analysis plan.

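### Dose proportionality is summarised only by pairwise exposure ratios with no stated reference value; one power-model slope per PK parameter would give a directly readable answer at almost no cost

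*SAP*

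**What the plan says.** SAP Section 7.5.2.3 is the only text in the SAP on dose proportionality. It sets the population ("The PK analysis of secondary endpoints will be based on the PKS"), names three PK parameters, and gives one output: "displaying geometric means of pairwise ratios together with 95% confidence intervals will be provided by dose group". It closes with "Additional PK, PKPD modelling will be defined in a separate analysis plan".

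The section does not say whether the ratios use raw or dose-normalised exposures, which pairs are formed, or what value would indicate proportionality. SAP Section 7 adds descriptive statistics for the PK parameters and says where inferential PK results will be reported. It does not mention dose normalisation or a dose-exposure regression.

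The design comes from SAP Section 6.1. "Patient randomisation will start with only adult patients to either 200 µg bid of BI 1265162 or placebo in a 1:1 ratio". After 28 patients, "the remaining patients will be allocated to the other doses of BI 1265162 as well as the highest dose and placebo in a 1:1:1:1:1 ratio", with 14 per arm. The intended overall split is described thus: "As a result, it was planned to have patients distributed in a 2:1:1:1:2 ratio". There are therefore four active doses. The only dose value that the SAP gives is 200 µg bid.

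**The concern.** Proportionality is a statement about the whole dose range: exposure rises as dose to the power 1. The plan answers with separate two-group comparisons. Two difficulties follow.

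- **Reading the ratios.** A raw ratio should equal the dose ratio of its pair under proportionality. A dose-normalised ratio should equal 1. Both tables would fit the text of Section 7.5.2.3, and a reader who takes one for the other reaches a wrong conclusion.
- **Combining the ratios.** Each parameter gets six overlapping intervals of unequal information, and the plan gives no rule for reading them together.

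At stake is how clearly a secondary PK result can be interpreted. The primary efficacy comparison is not affected.

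**Working it through.** The SAP states no sample size, power or acceptance range for dose proportionality, so there is no planned figure to reproduce.

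**Inputs from SAP Section 6.1.** Four active doses. Planned patients are 14 on each of the three lower doses and 28/2 + 14 = 28 on 200 µg bid, so 14 × 3 + 28 = 70 active patients.

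**Assumptions, not in the SAP.** Doses equally spaced on the log scale over a 10-fold range up to 200 µg, which makes neighbouring doses 10^(1/3) = 2.154-fold apart (ln 2.154 = 0.7675). Between-patient gCV 40% to 80%. Log-normal exposure, two-sided 95% intervals, and every active patient in the PKS.

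**1. Number of ratios.** Four doses give 4 × 3 / 2 = 6 pairs per parameter, and 6 × 3 = 18 over three parameters.

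**2. Reference values.** Under the power model, exposure = A × dose^b. A raw ratio estimates (d2/d1)^b and a dose-normalised ratio (d2/d1)^(b−1). If b = 1, the raw references are 2.15 (three pairs), 4.64 (two pairs) and 10 (one pair), and every normalised reference is 1. If b = 0.8:

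| Dose step | Raw ratio | Raw reference | Normalised ratio | Normalised reference |
|---|---|---|---|---|
| 2.15-fold | 1.85 | 2.15 | 0.86 | 1 |
| 4.64-fold | 3.41 | 4.64 | 0.74 | 1 |
| 10-fold | 6.31 | 10 | 0.63 | 1 |

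**3. Precision of a pair.** The log-scale SD is σ = √ln(1 + gCV²), which is 0.385 at 40% and 0.703 at 80%. The half-width of a log ratio is h = t × σ × √(1/n1 + 1/n2).

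- 14 v 14: t(26) = 2.056, so h = 2.056 × 0.385 × √(2/14) = 0.299, and 0.546 at gCV 80%. The interval is the estimate multiplied and divided by 1.35 to 1.73.
- 14 v 28: t(40) = 2.021, so h = 0.255, and 0.465 at gCV 80%. The factor is 1.29 to 1.59.

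Dividing h by the log dose ratio puts it on the slope scale:

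| Comparison | gCV 40% | gCV 80% |
|---|---|---|
| Neighbouring, 14 v 14 (÷ 0.7675) | ±0.39 | ±0.71 |
| Neighbouring, 14 v 28 (÷ 0.7675) | ±0.33 | ±0.61 |
| Lowest v highest, 14 v 28 (÷ ln 10 = 2.303) | ±0.11 | ±0.20 |

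**4. What a neighbouring pair can show.** If exposure is truly proportional, the expected 14 v 14 interval around 2.15 is 1.60 to 2.91 at gCV 40% and 1.25 to 3.72 at gCV 80%. Both exclude 1, the value for flat exposure. Neither excludes 1.85, the value for b = 0.8.

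**5. Precision of the power model.** Number the log-dose steps 0, 1, 2, 3 with 14, 14, 14 and 28 patients. The mean step is (14 + 28 + 84)/70 = 1.8. The sum of squares is 14 × (3.24 + 0.64 + 0.04) + 28 × 1.44 = 95.2, so Sxx = 95.2 × 0.7675² = 56.1. The half-width of b is t(68) × σ / √Sxx, with t(68) = 1.995:

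- gCV 40%: 1.995 × 0.385 / 7.49 = 0.10
- gCV 80%: 1.995 × 0.703 / 7.49 = 0.19

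**6. Smaller lower-dose arms.** With an assumed 6 patients per arm, a 6 v 6 ratio has a factor of 1.64 to 2.47. At gCV 80% the expected neighbouring interval under proportionality is then 2.154/2.47 to 2.154 × 2.47, or 0.87 to 5.32, which no longer excludes flat exposure.

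**The case against.** A reader might infer that the ratios are definitely raw. The SAP does not say so. SAP Section 3 builds on the protocol's statistical section, and the reference list includes an in-house paper on PK methods; either may define the ratios. What stands is that Section 7.5.2.3 is silent and does not cite that paper.

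A reader might also infer that every ratio has its own reference value. With equal log steps only three distinct dose ratios occur among the six pairs. A dose ratio is known and valid as a reference, and dividing by dose only rescales the ratio and its interval. Normalisation therefore makes the table easier to read but adds no information.

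The strongest objection concerns precision. The planned output already contains the lowest-v-highest ratio, whose slope half-width of 0.11 to 0.20 almost matches the power model's 0.10 to 0.19. It would be wrong to say that most of the ratios are uninformative, or that the plan cannot detect flat exposure at the planned sizes. This objection stands, and it limits the gain to readability and a small improvement in precision.

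Finally, further modelling is deferred to another plan, so a dose-exposure model is not ruled out. However, that sentence describes work additional to the proportionality summary and does not say that it covers proportionality.

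**Conclusion.** The point holds as a cheap improvement of low severity. Dose proportionality is named as the question, yet the section offers only six pairwise ratios per parameter, does not state whether they are dose-normalised, and gives no estimate that uses all doses.

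Under the assumptions above, neighbouring 14 v 14 pairs leave the slope uncertain by ±0.39 to ±0.71, enough to exclude flat exposure but not a slope such as 0.8. A pooled slope is known to ±0.10 to ±0.19, only slightly better than the widest pair.

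These sizes rest on assumed doses, gCV and full PKS membership, and on planned arm sizes that Section 6.1 reports in the past tense. SAP Section 7.4.1 leaves the lower doses out of the MMRM because they have too few patients. If those arms are smaller than 14, all the intervals widen, including that of the power model. The SAP attaches no hypothesis, acceptance range or decision to this result, so nothing stronger is warranted.

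**What to change.** In SAP Section 7.5.2.3, for each of the three PK parameters and each dose occasion N that is analysed:

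- Fit log(parameter) = a + b × log(dose) over all active dose groups in the PKS, and report b with its 95% CI against the reference value 1.
- Keep the pairwise geometric mean ratios as supportive. State that they are computed on dose-normalised values, so that 1 is the common reference.

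The cost is a few lines of SAP text and one regression per parameter and occasion, on data already collected. The drawback is the assumption that log exposure is linear in log dose; the retained pairwise ratios serve as a check on it.

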7.5.2.4 Analysis of Questionnaires (CASA-Q[©] and CFQ-R)

CASA-Q

The derivation of the CASA-Q domain scores will be performed according to the CASA-Q[©] user manual ([11](#)). All reported answers will be listed together with the derived domain scores.

Descriptive analysis will be done by treatment and domain score for baseline, Day 8, Day 29 and change from baseline.

CFQ-R

As no adolescent randomized, CFQ-R Teen/Adult version will be used.

The derivation of the CFQ-R scores will be performed according to the CFQ-R scoring instructions ([12](#)). The CFQ-R total score is the sum of each domain score. All reported answers will be listed together with the derived scores.

Descriptive analysis will be done by treatment and score for baseline, Day 29 and change from baseline and will be presented separately for total score and each domain score.

To explore the relationship between primary endpoint and CFQ-R respiratory domain score, a scatter plot of baseline CFQ-R respiratory domain score against change from baseline in FEV1 % predicted after 4 weeks of treatment.

7.7 EXTENT OF EXPOSURE

Extent of exposure to trial medication within the study will be displayed by treatment for the TS. Treatment exposure will be calculated as drug stop date - drug start date + 1 day.

7.8 SAFETY ANALYSIS

All safety analyses will be performed on the treated set.

7.8.1 Adverse Events

AEs will be coded with the most recent version of MedDRA.

The analyses of AEs will be descriptive in nature. All analyses of AEs will be based on the number of subjects with AEs and not on the number of AEs.

The analysis of AEs will be based on the concept of treatment emergent AEs. That means that all AEs occurring between first drug intake till 7 days after last drug intake will be assigned to the randomised treatment. All AEs occurring before first drug intake will be assigned to 'screening' and all AEs occurring after last drug intake + 7 days will be assigned to 'follow-up' (for listings only).

An overall summary of AEs will be presented. This overall summary will comprise summary statistics for the class of other significant AEs according to ICH E3 and for the class of adverse events of special interest (AESI). For the definition of AESI please refer to Section 5.2.6.1.4 of the CTP.

The frequency of subjects with AEs will be summarised by treatment (dose), primary system organ class and preferred term. AEs which were considered by the investigator to be drug related will be summarised separately. Separate tables will also be provided for subjects with serious AEs (SAEs), subjects with AESIs and subjects with other significant AEs (according to ICH E3). AEs will also be summarized by maximum intensity.

The system organ classes will be sorted according to the standard sort order specified by the European Medicines Agency (EMA), preferred terms will be sorted by total frequency (within system organ class).

A further table will present AEs by preferred term, dose group and intensity, sorted by descending relative frequency in any dose group.

Adverse events ongoing at Visits 2 (baseline), 3 (week 1) and 4 (week 4) will be provided to help explaining outliers regarding efficacy.

For disclosure of AE data on ClinicalTrials.gov, the frequency of subjects with non-serious AEs occurring with an incidence of greater than 5 % (in preferred terms) will be summarised by treatment, primary system organ class and preferred term. The frequency of subjects with SAEs will also be summarised.

For disclosure of AE data in the European union drug regulating authorities clinical trials (EudraCT) register, the frequency of AEs, the frequency of non-serious AEs with an incidence of greater than 5 % (in preferred terms) and the frequency of SAEs will be summarised.

7.8.2 Laboratory data

The analyses of laboratory data will be descriptive in nature and will be based on BI standards (6). If multiple reference ranges apply for one parameter (e.g. due to different age groups), analyses will be based on normalised values, which means transforming to a standard unit and a standard reference range. If references ranges are not available, analyses will be based on original values.

Laboratory data will be analysed both quantitatively as well as qualitatively. The latter will be done over comparing laboratory data to their reference ranges. Values outside the reference range will be highlighted in the listings.

Dose groups will be compared with descriptive statistics of laboratory values over time and by analysing differences from baseline. Additionally, frequency tables of changes between baseline and last values on treatment with respect to the reference ranges will be presented. Furthermore graphical representations over time will be generated for serum electrolytes.

Clinically relevant findings in laboratory data will be reported as AEs and will be analysed as part of AE analysis.

Spaghetti plots will display individual potassium over time.

